- May 2021: Comparators were adjusted to account for a phase 2 of the AHRQ Nursing Home intervention, which included additional "Community of Learning" sessions: we are comparing the 16-week AHRQ-funded COVID-19 ECHO followed by 9 weekly optional office hour sessions (ECHO), to the AHRQ-funded COVID-19 ECHO plus 17 weekly 60 minute sessions (ECHO plus). In addition, we added an additional secondary outcome, flu-like illness.

Our research and stakeholder team are expertly positioned to produce actionable findings towards our long-term objective to effectively improve infection control implementation in nursing homes through the following aims: **Primary Aim:** To compare the effectiveness of 16-week AHRQ phase 1 COVID-19 Project ECHO intervention (ECHO) followed by 9 weekly optional 60-minute office hour sessions (AHRQ phase 2) to the ECHO plus 17 additional 60 minute sessions (including an 8-week flu-focused refresher series for fall 2021) focused on infection control (ECHO plus) in reducing the number of nursing home residents with COVID-19. *We hypothesize that nursing homes engaged in the AHRQ ECHO plus intervention will have had 20% fewer COVID-19 infections than those in the AHRQ ECHO arm after 6 months.*

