**C. Study Design Overview:** A stratified cluster randomized design will be used. Using a 1:1 ratio, we randomly assigned 136 nursing homes (with approximately 16,700 residents) to: 1) AHRQ-funded COVID-19 ECHO that includes 16 weekly telehealth sessions addressing COVID-19 guidelines and best practices plus 9 weekly optional 60-minute office hour sessions or 2) AHRQ-funded COVID-19 ECHO plus 17 sessions with a focus on stakeholder identified needs and CDC infection control training. Randomization was stratified by geographic location (rural vs. urban), current COVID-19 infection rate (some vs. none), and facility capacity (<60 beds vs. ≥60 beds). Patient-centered outcomes (nursing home residents with COVID-19 infections, flu-like illness, hospitalizations, deaths, and QOL) will be assessed at baseline (intervention start date), 4, 6, 12, and 18 months. Our study is guided by the RE-AIM framework to critically evaluate both effectiveness and implementation outcomes of the proposed intervention. The RE-AIM framework is frequently utilized to improve sustainable adoption and implementation of effective, generalizable, evidence-based interventions

PRINCIPAL INVESTIGATOR (LAST, FIRST, MIDDLE): [name]

like Project ECHO. A formal study protocol will be developed upon funding (RQ-2). This protocol will further outline a data management plan that addresses data collection, organization, handling, description, preservation and sharing (IR-7).

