Q8. What is your facility doing to increase vaccine confidence and uptake among staff?

[figure not shown]
**Sample Size, Power, and Analytic Plan (IR-1):** The proposed study is a cluster randomization trial (stratified; RC-5). The intervention will be given at the cluster level (nursing homes). Study objectives and primary outcomes will be considered at both the cluster and individual levels (RC-1). There are several reasons why a cluster randomization was preferred over a traditional randomized controlled trial. First, the cluster randomization was preferred because the target of the intervention is a collective (i.e., a nursing home) rather than a particular patient. Second, cluster randomization was preferred due to potential contamination. Third, cluster randomization is compelling for practical reasons, when patient-specific level protocols would be nearly impossible like in the nursing home care (RC-2). The potential confounders will be balanced out by the randomization design. We will compare the observed confounders between two study arms and adjust them in the analysis if they are not balanced by design. Further, we will measure potential confounders before the start of exposure and report data on potential confounders with study results (CI-1; CI-4). We will monitor data collection for the RE-AIM metrics (surveys and interviews), routinely checking and following up with study sites to recover missing data (MD-1). We will use multilevel models such as mixed effects models or marginal models based on generalized estimating equation (GEE) method to estimate the intervention effect". Both methods are valid if the outcome data are missing completely at random. For data missing at random (i.e., depends on observed data only), mixed models can still provide valid inference and the weighted GEE methods will be considered to account for this type of missing data. We will also conduct sensitivity analyses to examine the robustness of results to missing data. Multiple imputation methods will be used to address the missing data in the covariates (MD-2, MD-4). Further, we plan to record and report all reasons for dropout and missing data and account for patients. Specifically, we will record reasons for missing data and perform analysis based on intention-to-treat principle as described below (MD-3). We have 126 nursing homes (62 in ECHO and 64 in ECHO plus) continuing to the phase 2 of the study. According to the CMS weekly data as of April 2021, the average weekly COVID-19 infection rate was 0.1%, average number of residents in nursing homes (cluster size) was around 75-80 and the coefficient of variation of cluster size was at about 0.76. Assuming 1% infection rate in the ECHO arm over the 9 weeks when additional topic sessions are provided in the ECHO plus arm, our study will have 80% power to detect a significant intervention effect if the infection rate is reduced to below 0.3% in ECHO plus arm. This calculation was based on a two-sided statistical test of difference between Poisson rates at alpha=0.05 and intracluster correlation coefficient (ICC)  $\leq 0.01$ . Our power will be below 80% if ICC is 0.05 or higher even if the infection rate is nearly zero in the ECHO plus arm. We will test the effectiveness of ECHO plus group by performing both individual-level analyses (primary) and cluster-level analyses (secondary) following the intention-to-treat principle. To account for intracluster correlations within nursing homes, we will use multilevel models such as mixed effects models or marginal models based on generalized estimating equation (GEE) method to estimate the intervention effect. The outcomes after 6-months of intervention will be analyzed using generalized linear models, with an appropriate link function depending on outcome type. Intervention effect on infection risk will be estimated as odds ratio or incidence

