
PRINCIPAL INVESTIGATOR (LAST, FIRST, MIDDLE): [name]

rate ratio based on logistic, Poisson or negative binomial regressions. State and cohort variations will be examined and accounted for using fixed or random effects in the models. Characteristics of residents (e.g., age, gender, cognitive function/dementia) and nursing homes (e.g., size, quality, baseline infection rate) will be adjusted. We hypothesize that the ECHO plus effect is heterogeneous and expect stronger intervention effects in subgroups without cognitive dysfunction/dementia as well as those who are younger (HT-1). Subgroup analysis with regard to key participant factors will be performed similarly to examine potential heterogeneity of intervention effects, further tested by interaction analysis (HT-2). If data are sufficient, we plan to explore the heterogeneity of intervention effect on infection rate based on the key participant factors such as age group, gender, dementia, insurance status, and race/ethnicity (HT-3). Outcomes will be assessed after the intervention is initiated (CI-3). Using all measures at 4, 6, 12 and 18 months, we will perform longitudinal analysis to evaluate if the intervention effect changes over time using the same modeling approach but add additional variables for time and time by intervention interaction. Correlations of repeated measures for the same resident will be taken into account in model estimation. Subgroup analysis with regard to key participant factors will be performed similarly to examine potential heterogeneity of intervention effects, further tested by interaction analysis. For cluster-level analyses, the aggregated outcomes (infection, hospitalization) are rates or proportions between 0 and 1 instead of being binary or count variables, we will use Beta regression to model them with a logit link function so that the coefficient can be interpreted as log odds ratio. We will also perform longitudinal analysis for aggregated outcomes based on Beta regression. All statistical tests will be two-sided, with p-values<0.05 considered statistically significant.

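### No section commits the randomisation factors to the outcome models; adjustment beyond an open list depends on observed imbalance, with no criterion, and this rule will rarely select rural/urban

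*Combined protocol and SAP*

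**What the plan says.** All the relevant text is in section C of the combined protocol and SAP.

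- **Study Design Overview.** "Randomization was stratified by geographic location (rural vs. urban), current COVID-19 infection rate (some vs. none), and facility capacity", with capacity split at 60 beds. The same paragraph defers detail: "A formal study protocol will be developed upon funding (RQ-2").
- **Sample Size, Power, and Analytic Plan, on balance.** The premise is "The potential confounders will be balanced out by the randomization design". The rule that follows is "We will compare the observed confounders between two study arms and adjust them in the analysis if they are not balanced by design". There is no list of the confounders meant, no test and no threshold. The plan does undertake to measure potential confounders before exposure begins and to report them with the results.
- **Same section, on the models.** "Characteristics of residents (e.g., age, gender, cognitive function/dementia) and nursing homes (e.g., size, quality, baseline infection rate) will be adjusted". Also "State and cohort variations will be examined and accounted for using fixed or random effects in the models". The factors named for exploring heterogeneity are all characteristics of residents.
- **Same section, on numbers.** "We have 126 nursing homes (62 in ECHO and 64 in ECHO plus) continuing to the phase 2 of the study".

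**The concern.** When randomisation is stratified, the analysis normally carries the stratification factors, so that the model's standard error reflects the balance the design has created. Here the plan makes no such commitment. Two of the three factors are covered in substance by examples in an open list, though not in the form used to stratify, and the third is covered by nothing.

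The rule that might fill the gap works the wrong way round for this purpose. It adds a covariate when the arms differ on it, and stratification is there to stop the arms differing on rural/urban. For other covariates, the rule makes the model depend on the realised allocation and on a criterion that can be picked afterwards. At stake are a little precision and the claim that the covariate set was fixed in advance.

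**Working it through.** **1. The plan's own figure.** The only design figure is 80% power for 1% against 0.3%, and this point does not depend on it. With 75 residents per home, CV 0.76 and ICC 0.01, the design effect is 1 + ((1 + 0.76²) × 75 − 1) × 0.01 = 2.173. Effective sizes are 62 × 75 / 2.173 = 2140 and 64 × 75 / 2.173 = 2209. Power is Φ(0.007 / √(0.01/2140 + 0.003/2209) − 1.96) = 0.813, and 0.824 with 80 residents per home. The stated 80% reproduces.

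**2. Stratification factors against the named model terms.**

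| Randomisation factor | Named for adjustment? |
|---|---|
| Current infection, some/none | As baseline infection rate, form not stated, in an open list |
| Capacity, <60/≥60 beds | As size, form not stated, in an open list |
| Rural/urban | No; state and cohort are named, but neither is rural/urban |

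**3. How often chance alone triggers adjustment.** For an unstratified home-level covariate with 62 and 64 homes, the standardised difference has standard deviation √(1/62 + 1/64) = 0.178.

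| Criterion for imbalance | Flagged by chance |
|---|---|
| p<0.05 | 5% |
| p<0.10 | 10% |
| Standardised difference >0.2 | 2 × (1 − Φ(0.2/0.178)) = 26% |
| Standardised difference >0.1 | 2 × (1 − Φ(0.1/0.178)) = 57% |

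For all 136 homes, taken as 68 per arm (an assumption), the last two are 24% and 56%.

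The rules p<0.05 and >0.1 disagree on one covariate with probability 0.575 − 0.05 = 0.525. With K independent candidates, the selected sets differ with probability 1 − (1 − 0.525)^K. That is 53% for K = 1, 89% for K = 3 and 99% for K = 6. K is an assumption; the documents give no number.

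**4. How often the rule would pick rural/urban.** In a simulation with assumed blocks of four in eight strata, 40% rural homes and 10 of 136 homes lost at random, rural/urban was flagged in 0% of trials at p<0.05 and at p<0.10. It was flagged in 0.1–0.2% at >0.2 and in 10–11% at >0.1.

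**5. What omission costs.** The same simulation ran 10,000 null trials per setting, with 126 homes, mean size 78, CV 0.76 and ICC 0.01. The control rate was the plan's 1%, or 2.6% (0.1% a week × 26 weeks). Further assumptions were half the homes with infection (rate ratio 1.5) and six other home-level covariates (rate ratio 1.15 per SD) that neither model contains. The core model held arm, log size and infection some/none. The fuller model added rural/urban and the 60-bed split.

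| Rate | Assumed rural/urban rate ratio | SE, core | SE, fuller | Reduction |
|---|---|---|---|---|
| 1% | 1.5 | 0.2967 | 0.2963 | 0.1% |
| 1% | 2 | 0.2875 | 0.2861 | 0.5% |
| 1% | 3 | 0.2792 | 0.2730 | 2.2% |
| 2.6% | 1.5 | 0.1762 | 0.1751 | 0.6% |
| 2.6% | 2 | 0.1671 | 0.1625 | 2.8% |

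Null rejection at the 1% rate was 0.050, 0.043 and 0.038 for the core model against 0.048, 0.045 and 0.046 for the fuller one (Monte Carlo error about 0.2 points).

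A separate, simpler illustration used a continuous home-level outcome, 126 homes and 40% in one stratum. Leaving out a stratification factor that explains 2%, 5%, 10% or 20% of between-home variance gave type I error of 0.048, 0.048, 0.041 and 0.029. Power was 0.79, 0.78, 0.76 and 0.72, against about 0.79–0.80 with adjustment. Both exercises show a conservative test, more so as the omitted factor becomes stronger.

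**The case against.** The strongest reply is that little is wrong in practice. The plan adjusts without condition for size, baseline infection rate, quality, age, gender and cognitive function, and it models state and cohort. The trigger then matters only for covariates beyond that core, and the documents name none. The open list does not exclude rural/urban. Potential confounders are to be measured before exposure and reported. A formal protocol was to follow and could contain the closed list.

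Most of this stands, and it is why the point is minor. The two statements can be read together as a core set plus triggered additions. What does not stand is the inference that the covariate set is therefore fixed. The core is given by example, the additions have no criterion, and no text commits to rural/urban. The deferral to a later protocol helps only in part: this text already reports the completed randomisation and the homes entering phase 2, and still leaves the list open.

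A reader might go further and infer that omitting rural/urban biases the comparison or inflates type I error. The documents do not support that: the factor is balanced by stratification, and omission makes the test conservative.

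**Conclusion.** The point holds as a minor one. The randomisation factors are not committed to the models, rural/urban is named in no covariate list, and the balance-triggered rule has no criterion and is poorly suited to picking up a stratified factor. The gain from including the factors is small: a standard error about 0.1% to 2.8% lower, on assumed rural/urban rate ratios of 1.5 to 3 and a core model that leaves out quality, state, cohort and resident covariates. The flag rates of 5% to 57% need only the plan's home counts and a normal approximation.

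A reader might also infer that the choice of criterion could shift the rate ratio by a material part of the hypothesised effect, that ECHO plus homes "will have had 20% fewer COVID-19 infections than those in the AHRQ ECHO arm after 6 months". That would require assuming how many further covariates there are and how strongly they predict infection. The documents give neither, so no size is claimed for the movement in the estimate.

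**What to change.** In the Sample Size, Power, and Analytic Plan, replace the balance-triggered sentence with:

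> All effectiveness models include the three randomisation factors as fixed covariates, whatever the observed balance; baseline comparisons are descriptive only and do not determine adjustment.

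Three details need settling with it:

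- Enter capacity and baseline infection once each, in one prespecified form (the stratification category or the continuous version), so that neither appears twice.
- List the remaining covariates in full before outcome data are analysed, here or in the formal protocol if that is the governing text.
- Use resident-level covariates (age, gender, cognitive function) only in models fitted to resident-level data. In the cluster-level Beta regressions, use defined facility summaries or leave them out.

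The cost is one to three degrees of freedom among 126 homes, plus the drafting of the closed list and any facility summaries. The three factors were recorded for randomisation, so no new data are needed. The change does not settle the other open modelling choices, such as mixed model or GEE and logistic, Poisson or negative binomial regression.

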**Study Population and Setting (RQ-3; PC-2):** We recruited 136 nursing homes from national nursing home lists, focusing primarily in Pennsylvania (PA), but including other sites within the northeast and Midwest from states that are demographically and geographically similar, including Connecticut, New Jersey, New York, Wisconsin, New Hampshire, Illinois, Vermont, Indiana, Virginia, Maryland, and Ohio. (CI-2). Given the differences in nursing home types and how they impact effective programming, our project focused on skilled nursing facilities eligible for the AHRQ-funded ECHO program. Nursing homes were recruited through collaborations with our stakeholders, including multiple state agencies (Department of Health-DOH, Department of Human Services-DHS, Department of Aging-DA) and state nursing home organizations (PA Healthcare Association, Leading Age PA) through phone calls and emails. COVID-19 ECHO participants include two nursing home staff members as required by the AHRQ program, and we encouraged participation by infection control staff and other facility leadership (e.g., medical director, nursing, administrators). Participants in our pilot study (n=16) and those who may have participated in any COVID-19 focused Project ECHO series will be excluded. These 112 nursing homes have already been offered the opportunity to participate in either Penn State's pilot AHRQ-funded ECHO cohort or by our colleagues at Wellspan Health. We were confident in the willingness of nursing home staff to participate in weekly, 90-minute ECHO sessions (the last 30 minutes are optional) over the proposed study period, as we have already piloted this weekly program early in the pandemic, resulting in 80% of participants (27 of 34) attending every week over the 6-week timeframe. Further, we have partnered with multiple state and local nursing home stakeholders who have shared with us in our conversations the critical nature of this intervention and the eagerness for nursing homes to be engaged to access this information. Although many stakeholders mentioned this, the feedback was particularly strong from [name], Director of Quality Initiatives for the Pennsylvania Healthcare Association, whose organization engages 200 nursing homes and 400 members and has a national umbrella organization through which to reach nursing homes in additional states. We are confident that through our conversations with our 16 stakeholders who provided letters of support for our proposal, including nursing home staff and administrators, three state agencies, three state professional organizations, and healthcare systems, we have a finger on the pulse of participant willingness to engage. Willingness to engage in ECHO is also strengthened by our overwhelmingly positive response to our pilot series. Half of these participants reported never participating in an ECHO series previously yet rated the experience highly as more powerful than traditional learning. These responses highlight the belief in the intervention and will strengthen willingness to participate regularly.

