**Effectiveness:** The *primary outcome* is COVID-19 infection rate reduction in nursing homes. This de-identified patient data will be obtained using The Nursing Home COVID-19 Public File along with three *secondary outcomes*: flu-like illness, COVID-19 hospitalizations, and deaths. Secondary outcomes will be collected through the National COVID-19 Nursing Home data file that is publicly available (<https://data.cms.gov/stories/s/COVID-19-Nursing-Home-Data/bkwz-xpvg>). Specifically, the variables that will be assessed include: Residents Weekly and Total Admissions, Residents Weekly and Total COVID-19 Deaths, Number of Residents with New Influenza, and Number of Residents with Acute Respiratory Illness Symptoms Excluding COVID-19 and/or Influenza. This data is also available for staff. Nursing home resident QOL (*secondary outcome*; PC-3) will be measured using CMS' Minimum Data Set, including emotional, symptom and functional statuses, behavioral disturbances, social support, patient engagement, and shared decision making. CMS data will be linked to residents at participating nursing homes (IR-3). We will collect several measures to assess how much COVID-19 ECHO is utilized in nursing homes (see attached Excel spreadsheet). Our Aim 2 proposed using the RE-AIM framework to critically evaluate the utilization of interventions in both trial arms. To accomplish this, for example, we will record and categorize participation in each session (e.g., number of staff per nursing home site, role of participants in nursing homes, engagement in sessions). At the beginning of each ECHO session, we ask that all participants place their name, email address, and affiliation in the chat box. In addition, we can pull zoom reports to identify participants and the length of time they joined each session (to ensure full participation). We will also offer continuing education credits, which is a second opportunity to record engagement and assess quality dimensions that explain participation (e.g., satisfaction, acceptability). Surveys at the end of the cohort will also provide feedback as to the utilization of best practices taught throughout ECHO sessions. Lastly, as described in the interviews, we will have questions specifically identifying how engagement in ECHO changed practice. Equally important, all data collection is guided by the RE-AIM framework in order to provide a complete picture of how ECHO facilitates practice change and supports adoption of best practices. **Implementation outcomes:** We will measure Reach by assessing the characteristics of nursing homes and staff who participate in the study and those who do not. We will then compare these data to the overall characteristics of PA nursing homes to assess representativeness. We will evaluate Adoption by assessing the characteristics of early adopters

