
PRINCIPAL INVESTIGATOR (LAST, FIRST, MIDDLE): [name]

as well as barriers and facilitators (i.e., inner and outer contexts, Organizational Readiness for Implementing Change scale [ORIC], Practice Adaptive Reserve scale [PAR], Change Process Capacity Questionnaire [CPCQ]).

Table 4. Proposed Study Outcomes

Study Outcomes	Description	Data Source (Timing of Assessment)
Reach	Absolute number, proportion, and representativeness of nursing homes and staff who agree to participate	Study recruitment logs and staff survey (baseline)
Effectiveness	Primary outcome: COVID-19 infection rate reduction; Secondary outcomes: flu-like illness, hospitalizations, deaths, QOL	National COVID-19 Nursing Home data file and CMS Minimum Data Set (baseline, 4, 6, 12, 18 months)
Adoption	Absolute number, proportion, and representativeness of nursing homes and staff who initiate and complete the ECHO series; and barriers and facilitators for adoption	Study participation logs; staff survey (baseline, 6 months) with validated measures including ORIC, PAR, and CPCQ; and key informant interviews (6 months post intervention)
Implementation	Nursing home staff knowledge and attitudes towards the various intervention functions and components, their level of implementation, and barriers and facilitators for implementation	Selected items from CDC's Preparedness Checklist; staff surveys (baseline, 6, 12 months) with validated measures; and key informant interview (6 months)
Maintenance	Extent to which implemented guidelines for emergency preparedness in an infectious disease outbreak become part of nursing home policies post-intervention	Key informant interview (12 months)

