### I. Risks to Human Subjects

a. *Involvement of Human Subjects:* The proposed study includes human subjects in its research but poses no more than minimal risk. We will recruit a total of 200 nursing homes to participate in the proposed randomized controlled trial. We anticipate enrolling at least one representative from each nursing home, which may include administration, director of nursing, or infection control staff to participate in ECHO sessions if the nursing home is randomized to the intervention group. We anticipate including de-identified data to assess our primary outcome (COVID-19 infection rate reduction) from the publicly available PA COVID-19 Nursing Home Reporting System. *Sources of Materials:* This study's primary outcome will rely on de-identified data from a publicly available source (The Nursing Home COVID-19 Public File), in aggregate, describing de-identified nursing home resident cases of COVID-19, hospitalizations and death. Additionally, we will obtain identifiable nursing home resident data through PSU's secure access to Medicare data through the Administrative Data Accelerator. Data analysis by investigators will occur through secure remote computing. Given our reliance on only secondary data for nursing home residents' outcomes, they will not be required to consent to participation. However, we will create and share messaging to make them aware of the study for dissemination at the nursing home level. The data will be used for research purposes only.

b. *Potential Risks:* The minimal risks to human subjects in the proposed project include loss of confidentiality.

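### The secondary cluster-level Beta regression cannot take homes with zero cases and no zero rule is given; separately, infection is not assigned to any of the planned resident-level data that the primary model's covariates need

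*Combined protocol and SAP*

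**What the plan says.** All references are to the Combined protocol and SAP.

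**Models.** Sample Size, Power, and Analytic Plan (IR-1) announces "performing both individual-level analyses (primary) and cluster-level analyses (secondary) following the intention-to-treat principle". Infection effects are to be odds ratios or incidence rate ratios from logistic, Poisson or negative binomial regression. The models adjust for resident characteristics (age, gender and dementia are the examples) and for home characteristics. Stronger effects are predicted in younger residents and in those without dementia. The longitudinal analysis allows for correlation within a resident. For the cluster-level analysis, infection and hospitalisation become proportions modelled by Beta regression with a logit link, cross-sectionally and longitudinally. Zeros are not mentioned.

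**Sources for infection.**
- Outcomes, Effectiveness: "This de-identified patient data will be obtained using The Nursing Home COVID-19 Public File". The same paragraph adds that "CMS data will be linked to residents at participating nursing homes", directly after describing quality of life.
- Table 4, one row for all effectiveness outcomes: "National COVID-19 Nursing Home data file and CMS Minimum Data Set (baseline, 4, 6, 12, 18 months".
- Protection of Human Subjects, I.a, first statement: the primary outcome comes "from the publicly available PA COVID-19 Nursing Home Reporting System".
- Same section, next statement: the "primary outcome will rely on de-identified data from a publicly available source (The Nursing Home COVID-19 Public File), in aggregate". It then says "we will obtain identifiable nursing home resident data through" the university's Medicare access, with no outcome attached.
- Project Plan and Timeline: the Minimum Data Set appears only against quality of life, with a 15-month delay. Early results from 6-month outcomes are scheduled in year 1.

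**The concern.** A Beta density lives strictly between 0 and 1. At 0 its logarithm is minus or plus infinity depending on the shape parameter, so a home with no cases cannot enter the likelihood. If such homes are common, the cluster-level analysis cannot be run as written, and the analyst must pick a workaround after the data are in. Two common ones are dropping the zeros and squeezing every proportion slightly into the interior. Both discard or dilute the information that an infection-control intervention is meant to produce, namely homes with no cases.

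The second issue concerns the primary analysis. Age, gender and dementia adjustment needs infection status by resident. The plan describes its infection file as aggregate and never says which of its resident-level data sets, if any, carries infection. Left open, the choice between a resident-level and a facility-count model, with different covariates, could be made after results are visible.

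**Working it through.** **Inputs** (Sample Size, Power, and Analytic Plan): 62 ECHO and 64 ECHO plus homes; mean size 75 to 80 (77.5 used); coefficient of variation of size 0.76; 1% versus 0.3% over 9 weeks; ICC up to 0.01; weekly rate 0.1%. The 20% reduction is the Primary Aim's hypothesis. For 26 weeks I assume a constant rate: 26 × 0.1% = 2.6% in ECHO and 0.8 × 2.6% = 2.08% in ECHO plus.

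**1. Reproduce the plan's power.** Design effect = 1 + [(0.76² + 1) × 77.5 − 1] × 0.01 = 2.213. Effective residents: 62 × 77.5 / 2.213 = 2,172 and 64 × 77.5 / 2.213 = 2,242. SE = √(0.01/2,172 + 0.003/2,242) = 0.00244. Power = Φ(0.007/0.00244 − 1.96) = 81.9%. The stated 80% reproduces, so the rates are a fair basis for counting zeros.

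**2. Homes with no cases** (independent cases, equal sizes; P(0) = exp(−rate × 77.5)).
- 9 weeks: 62 × 0.461 + 64 × 0.793 = 28.6 + 50.7 = 79.3 of 126.
- 26 weeks: 62 × 0.133 + 64 × 0.199 = 8.3 + 12.8 = 21.0 of 126.

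With ICC 0.01 and variable home sizes (simulation below) the means are 92.8 and 45.5.

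**3. Why the workarounds shrink the effect** (same simple setting).
- Dropping zeros: the mean proportion among the remaining homes is rate / (1 − P(0)). At 9 weeks, 0.003/0.207 = 1.45% against 0.01/0.539 = 1.85%, a ratio of 0.78 instead of 0.30. At 26 weeks, 0.0208/0.801 against 0.026/0.867 gives 0.87 instead of 0.80.
- Squeezing by (125y + 0.5)/126: at 9 weeks, (0.375 + 0.5)/(1.25 + 0.5) = 0.50. At 26 weeks, (2.6 + 0.5)/(3.25 + 0.5) = 0.83.

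The fitted Beta model moves further toward 1 than these means at 9 weeks.

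**4. Fitted models by simulation.** Assumed: gamma-distributed sizes (mean 77.5, CV 0.76, minimum 5) and beta-binomial counts; equal sizes at ICC 0. Covariates had either no effect or a rate ratio of 1.5 per stratum plus state variation. There were 1,000 trials for Beta and 2,000 for Poisson. Estimates are ranges of medians over ICC 0 to 0.01; rejection rates are at ICC 0.01.

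| | 9 weeks, true 0.30 | rejects | 26 weeks, true 0.80 | rejects |
|---|---|---|---|---|
| Beta, zeros dropped | 0.80–0.85 | 5–7% | 0.88–0.91 | 8–9% |
| Beta, squeezed | 0.64–0.79 | 43–72% | 0.83–0.89 | 11–16% |
| Poisson, facility counts | 0.29–0.30 | 78–81% | 0.80 | 18–19% |

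In one further setting, ICC 0 with variable sizes at 9 weeks, dropping gave 0.75. With independent cases and equal sizes, squeezing costs almost no power (98–99% against 99% at 9 weeks; 37% for both at 26 weeks), but the estimate is still pulled toward 1. Null rejection of the adjusted Poisson at ICC 0.01 was 4.2–5.1% with a small-sample correction and 6.9–7.4% without. The plan gives no hospitalisation rate, so its zeros cannot be counted.

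**5. What facility counts can support.**

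| Element of the plan | From facility counts? |
|---|---|
| Arm effect at 6 months (Poisson or negative binomial) | Yes |
| Home-level adjustment | Yes |
| Resident age, gender, dementia adjustment | No |
| Resident subgroups for infection | No |
| Within-resident correlation (longitudinal analysis) | No |

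The recruitment text describes sites "focusing primarily in Pennsylvania (PA), but including other sites within the northeast and Midwest" and lists 11 states besides Pennsylvania, so a Pennsylvania system cannot cover all 12.

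**The case against.** **The primary model is not unfittable.** A reader might infer that the primary analysis cannot be carried out, or that the trial has no resident-level data. The documents support neither. Facility counts yield an arm effect with models the plan lists. The within-resident correlation sentence serves the longitudinal analysis, and some subgroup work is conditional on sufficient data. Linked CMS data, the Minimum Data Set and identifiable Medicare data are all planned; they are unassigned, not absent. The Study Design Overview also defers data handling to a later formal protocol. All of this stands. What remains is that the covariates are already fixed while their infection source is not. If the Minimum Data Set were meant, its 15-month delay would have to be squared with 6-month results in year 1.

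**The Pennsylvania system looks like leftover text.** The same paragraph still speaks of 200 homes and of sessions only for homes randomised to the intervention. Most other statements name the national file. This is probably editorial, but it still needs correcting.

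**Zero-inflated Beta regression would also work.** In 300-trial runs its marginal mean ratio was 0.31 to 0.33 against 0.30 at 9 weeks, and 0.81 to 0.83 against 0.80 at 26 weeks. This stands: the defect is the missing zero rule, and Poisson is not the only cure.

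**The large distortions belong to the 9-week power scenario.** Also true. The planned assessments are at 4, 6, 12 and 18 months.

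**Conclusion.** The Beta regression is wrong as written for aggregated infection. It cannot accept zero-case homes, and on the plan's figures these are roughly 63% to 74% of homes over 9 weeks (79/126 to 93/126) and 17% to 37% over 26 weeks (21/126 to 46/126). The two simple workarounds bias toward no effect, severely at 9 weeks and modestly at 6 months, where the power difference is small and every model is underpowered. Only the secondary analysis is affected, so it would be wrong to infer that the primary result is biased by this.

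The source statements need reconciling: resident adjustment and resident subgroups for infection have no assigned data, although an arm effect remains estimable.

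The sizes rest on the assumed home-size distribution, a constant weekly rate, and a 20% reduction over the whole 26 weeks. That last assumption is generous, because both arms receive the same 16-week Phase 1. If the effect began only after week 16, the 26-week cumulative ratio would be (1.6 + 0.8)/2.6 = 0.92. The zero problem itself does not depend on these choices.

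**What to change.** 1. **Cluster-level analysis.** Replace Beta regression, including its longitudinal version, with a Poisson model of cases per home. Use the log of resident-weeks as offset, over the same stated accrual window as the outcome; home-level robust errors with a small-sample correction; and the rate ratio as effect measure. Keep negative binomial as a sensitivity analysis. Confirm that the software really applies the correction. A zero-inflated Beta model reported as a marginal mean ratio is an acceptable alternative.
2. **Primary infection analysis.** Choose one of two routes now. Either name the resident-level infection source, with case definition, linkage and a timing that fits the 6-month analysis; or make the facility-count Poisson model primary with facility-level covariates only: the three stratification factors, baseline infection rate, quality, cohort, and Pennsylvania versus other states as a fixed term. On the second route, resident-adjusted and subgroup infection analyses become secondary, conditional on such a source.
3. **Human Subjects section.** Delete the Pennsylvania-only system as a source for the primary outcome.

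The cost is wording in the analysis plan. The models are already listed, and Poisson matches the basis of the power calculation. The price is that resident-level adjustment may leave the primary analysis. Low power at 6 months (about 18–19% for a 20% reduction at ICC 0.01) is not cured.
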